6. ANALYSIS POPULATIONS

6.1. Modified Intention-To-Treat population (mITT)

The mITT population will consist of all randomized subjects who have received at least a single dose of the investigational product. The mITT population will be used for all efficacy analyses. In the event of a discrepancy between the randomized treatment and the actual treatment received, subjects will be analysed according to the randomization treatment.

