To assess the impact of the above “treatment failure” rule, the missing data strategy will employ the control-based multiple imputation (MI) procedure and delta-based multiple imputation (or tipping point analysis) to assess the sensitivity of the study conclusions to the missing response data. Multiple imputation provides a better estimate of the effect of missing data on the variance of the estimates and is therefore less likely to result in false positive inferences. Control based imputation restricts imputing responses for the active arm participants to responses in the control arm. This process will be done sequentially for each time point with missing responses. The process is described by Ratitch & O’Kelly (2011)⁶ and summarized below. These methods will be implemented in SAS9.4® using PROC MI and PROC MIANALYZE and are based on pattern mixture models that assume monotone drop out.

In order to meet the monotone assumption, if there are intermittent missing data points, these will be first imputed using a Monte Carlo Markov Chain Method (MCMC). Please refer to [Appendix](#).

Intermittent missing data is typically a very small percentage of overall missing and is not expected to affect or bias inference. The MI procedure will be used for subjects with missing Week 14 WI-NRS data and/or who withdraw prematurely prior to Week 14.

8.6.1.1 Control Based Imputation.

The monotone missing data is sequentially imputed using the responses of the control group only. This is done sequentially for each time point. In order to ensure that only the control group data is used for active arm subjects with responses missing starting at time t1, the data set is subset to include all control subjects and only those active arm subjects who have missing values at time t. This is repeated for each time point going forward – please refer to [Appendix](#) for details.

PROC MI is then used to impute all missing values for t1 in the treatment arm using the standard PMM imputation approach. Please refer to [Appendix](#) for details.

The data set is combined with the rest of the data and a new subset is created for active arm recipients with responses missing for time t2. This is repeated for each subsequent time point.

Finally, each fully imputed data set is analyzed using the appropriate procedure, e.g., Proc Mixed, and then the results are collated using PROC MIANALYZE.

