12 APPENDIX

12.3 Programming Guidance Document for Multiple Imputation, Control –based Imputation & Tipping Point Analysis

Introduction.

This appendix describes three approaches to multiple imputation.

1. Simple Multiple Imputation;
2. Control- based Imputation;
3. Tipping Point Analysis.

All of these are being implemented in data sets that have repeated measures data collected from subjects at multiple time points.

The primary efficacy endpoint is defined as the difference between the percentage of “Responders” at Week 14 for the NAL ER treatment arm versus the placebo arm. A “Responder” is defined as a subject with a ≥ 4 -point decrease in the 7-day average WI-NRS from baseline to Week 14.”

Secondary endpoints are:

- The mean change in ItchyQoL from baseline to Week 14 for the NAL ER treatment arm versus the placebo arm;
- Change in PAS as assessed by the percentage of subjects having a 1-category improvement in the percentage of prurigenous lesions with excoriations/crusts (item 5a) from baseline to Week 14 for the NAL ER treatment arm versus the placebo arm;
- The mean change in sleep disturbance (PROMIS Sleep Disturbance Short Form 8a) from baseline to Week 14 for the NAL ER treatment arm versus the placebo arm.

Multiple imputation is a missing data approach that assumes that the missing data is missing at random (MAR), i.e., that the probability of missing is not a function of the values that are missing but only depend on the observed responses.

The advantage of MI over single imputation is that it allows one to adjust the variance to account for the imputation of the missing data.

All of the data sets on which imputation is applied are longitudinal data sets, specifically the following ADaM datasets: ADEFF and ADQS. Please note: ADEFF will use 4 visits (AVISITN 2-5/ Week 2, 6, 10, 14)

ADQS will use 3 visits (AVISITN 3-5/Week 6, 10, 14).

The following is an explanation of the process.

This is a guidance document. It does not provide the exact code to be implemented but describes the processes & principles that need to be followed in order to implement these analyses.

There are five steps in simple MI process.

1. Check missing data patterns;
2. Impute non-monotonic / intermittent data – leaving only monotone missing data;
3. Use monotone regression to impute monotone missing data & create multiply imputed data sets;
4. Run the efficacy analyses (PROC GENMOD, PROC MIXED) on the multiply imputed data sets;

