5. Use PROC MIANALYZE to combine the efficacy output to get a single estimate from all the imputed data sets.

Step 1. Checking missing data patterns

For this study, the missing data patterns will be checked by treatment and visits 3 to 5.

There are 3 steps to this process:

Create dataset for efficacy measure including visits from baseline to week 14

```
data mi_chk1; set datax;
where param="" and paramcd="" and dtype="" and 3 <= visit <=5;
run;
```

Transpose dataset to display each visit as one column:

```
proc sort data = mi_chk1; by treatment_id;
proc transpose data=mi_chk1 out=mi_chk2 prefix="";
by treatment_id;
id avisitn;
var aval;
run;
```

Use PROC MI with the NIMPUTE=0 option to create the "Missing Data Patterns" table for the specified variables:

```
ods output MissPattern=missp;
proc mi data=mi_chk2 NIMPUTE=0;
  by treatment;
  var visit3 – visit5;
run;
/*Add baseline to estimate change from baseline*/
```

```
proc sort data = mi_chk1; by id; data base; set mi_chk1 (Keep = id base country); by id; if first.id;
run;
proc sort data = mi_chk2; by id;
proc sort data = base; by id;
data mi_chk2; merge mi_chk2 base; by id;
run;
```

Step 2: Impute non-monotonic / intermittent data – leaving only monotone missing data.

Fill in the intermittent missing data using the following code.

```
proc sort data = mi_chk2; by treatment;
proc mi data=mi_chk2 seed=12345 NIMPUTE=50 out=MI;
by trt01pn;
mcmc impute=monotone;
var Visit3 – Visit5;
run;
```

Step 3. Use monotone regression to impute monotone missing data & create multiply imputed data sets.

Here the non-missing values for subjects in the control group are used to impute values for the subjects with missing values in the control group and similarly for the subjects in the active treatment group.

**Visit 3 values are imputed using baseline value and treatment;
visit 4 values are imputed using baseline, treatment and visit 3 & so on.**

```
proc sort data = mi; by _Imputation_;
proc mi data=mi out=mi_reg seed=54321 nimpute=1;
by _Imputation_;
var trt01pn base v3 v4 v5;
class trt01pn;
monotone regression;
run;
```

Convert the data set from a horizontal dataset, i.e. one row per subject to a vertical data set, i.e., multiple rows per subject.

```
Data mi_reg1; set mi_reg;
Visit = 1; WINRSA=base; output;
Visit = 2; WINRSA=v3; output;
visit = 3; WINRSA=v4; output;
visit = 4; WINRSA=v5; output;
drop v3 v4 v5;
run;
```

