In this analyses, the concept is to assess the level of bias introduced by the missing at random assumption in the first simple MI performed above. In this approach, subtract a pre-determined value from the imputed values for the actively treated group. this approach uses the standard deviation of the scores for the completers in the treated group. It could be a %change in the mean or a variety of other values depending on the expected effect. The suggested approach is below.

```

data mi_chk1; set adeff;
where param="WINRS Average" and paramcd="WINRSA" and dtype="" and 2 <=avisitn<=5;
run;
data mi_chk1; set mi_chk1;
if trt01pn = 1 then trt = 1;
else if trt01pn = 2 then trt = 0;
run;

proc sort data = mi_chk1; by trt usubjid;
proc transpose data=mi_chk1 out=mi_chk2 prefix=v;
by trt usubjid;
id avisitn;
var aval;
run;
  by trt ;
  var v2-v5;
run;

```

Next estimate the standard deviation of the WINRS score in the control group and active treatment group by visit among those subjects who completed all visits.

Then merge a data set with the delta value to the data set where values will be imputed.

Use proc univariate to obtain the mean values, stddev, range for the completers in the treated group in order to identify a delta value (SD in this case. Other approaches could use the median, or percentiles).

Suggested code is below.

```

proc sort data = mi_chk1; by usubjid;
data base; set mi_chk1 ( Keep = usubjid base country complfl); by usubjid; if first.usubjid;run;
proc sort data = mi_chk2; by usubjid;
proc sort data = base; by usubjid;
data mi_chk2; merge mi_chk2 base; by usubjid;
run;
proc univariate data = mi_chk2; where complfl = 'Y'; by trt;
var v2 v3 v5 v5;
output out=WINRSCOMP_uni mean=Meanv2 Meanv3 meanv4 meanv5
      std=stdv2 stdv3 stdv4 stdv5
      range=range_v2 range_v3 range_v4 range_v5;
run;

```

```

proc sort data = WINRSCOMP_UNI; by trt;
data mi_chk3; merge mi_chk2 winrscomp_uni; by trt;
run;
  
```

Fill in the intermittent missing data using the following code.

```

proc sort data = mi_chk3; by treatment;
proc mi data=mi_chk3 seed=12345 NIMPUTE=50 out=MI;
  by trt01pn;
  mcmc impute=monotone;
  var Visit2 – Visit5;
run;
  
```

Create an id variable to identify which visits were imputed in the active treatment group.

```

data control_mi; set mi; where trt = 0; run;
data NALER_mi; set mi; where trt = 1;
Data NALER_MI; Set NALER_MI;
if V2 = . then Imp_v2 = 1; else Imp_V2 = 0;
if V3 = . then Imp_v3 = 1; else Imp_v3 = 0;

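### As printed, the SAP 12.3 code draws both subjects and baselines from filtered post-baseline rows, so mITT subjects with no value in that range can be left out of the imputation

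*SAP*

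**What the plan says.** SAP 6.1 defines mITT as randomized subjects with at least one dose, with no post-baseline value required, and states: "The mITT population will be used for all efficacy analyses". The sensitivity text in SAP 8.6 (Analysis of Primary Efficacy Endpoint) sets the scope of imputation: "The MI procedure will be used for subjects with missing Week 14 WI-NRS data and/or who withdraw prematurely prior to Week 14". SAP 8.6.1.2 goes further and describes subjects missing from Week 2 onward whose imputed values are then shifted by delta.

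The code in SAP 12.3 works as follows.

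- **Step 1** keeps rows by "where param='' and paramcd='' and dtype='' and 3 <= visit <=5" and transposes them to one row per subject.
- **Baseline** is taken from the same filtered file, "data base; set mi_chk1 (Keep = id base country); by id; if first.id", and joined by "data mi_chk2; merge mi_chk2 base; by id".
- **Step 3** has Visit 3 predicted from baseline and arm.
- **Control-based imputation** reuses these steps and expects Visit 3 to be complete once intermittent gaps are filled.
- **Tipping point** filters WI-NRS to visits 2 to 5 and again takes baseline from the filtered rows: "data base; set mi_chk1 ( Keep = usubjid base country complfl); by usubjid; if first.usubjid;run".

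On visit ranges, the SAP 12.3 introduction says "ADEFF will use 4 visits (AVISITN 2-5/ Week 2, 6, 10, 14" and "ADQS will use 3 visits (AVISITN 3-5/Week 6, 10, 14". For WI-NRS, the first of these disagrees with the Step 1 filter.

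**The concern.** Both inputs to the merge come from one filtered file, so they hold the same subjects. No step starts from the mITT list. A subject who took a dose and left before the first visit in the range has no row to transpose and no baseline to carry, so nothing is imputed.

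The primary model in SAP 8.6 also uses only observed responses from visit 3 on and leaves missing Week 14 values missing, so it omits these subjects too. Control-based imputation and the tipping point are the planned checks on that omission. If the control-based file holds only the subjects the primary model already used, it cannot test the effect of early loss. Protocol 9.3 expects gastrointestinal and nervous-system effects to come on early and to make some subjects stop, so early loss could well be greater on NAL ER.

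The guidance also points both ways. Step 3's rule for Visit 3 is needed only for subjects with Visits 3, 4 and 5 all missing, because the monotone fill completes Visit 3 for anyone with a later value. The control-based section's expectation that Visit 3 is complete holds only if those subjects are absent.

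**Working it through.** **The plan's own figure.** SAP 5.2 gives 234 subjects without site in the model (25% versus 45%, two-sided 0.05, 90% power). The pooled two-proportion formula gives n per arm = [1.960 × √(2 × 0.35 × 0.65) + 1.282 × √(0.25 × 0.75 + 0.45 × 0.55)]² / 0.20² = (1.322 + 0.845)² / 0.04 ≈ 117.4, rounded up to 118, or 236 in total. This is consistent with 234. The point does not rest on it; it only confirms the response rates used below.

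**Who enters the file.** The filter, transpose, first-row baseline and merge were run on five toy subjects, with rows present only where data exist.

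| Toy subject | Step 1 filter (visits 3-5) | Tipping-point filter and ADEFF text (visits 2-5) | File started from mITT |
|---|---|---|---|
| A: complete | in | in | in |
| B: last value at Week 6 | in | in | in |
| C: Week 2 only | lost | in | in |
| D: no post-baseline value | lost | lost | in |
| E: off drug, returns at Week 14 | in | in | in |

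If the data sets carry blank scheduled-visit rows, all five enter under either filter. Without blank rows, the tipping-point flag for an imputed Week 2 value can never be set. After the monotone fill, Week 2 is missing only for subjects like D, and D is not in the file.

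**Size, as an illustration.** Inputs:

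- 180 per arm, the maximum in SAP 8.8.1.
- Response of 45% (NAL ER) and 25% (placebo) among retained subjects, borrowed from the design assumptions in SAP 5.
- An assumed share d of NAL ER subjects with no value in the range. The documents give no such share.
- Control-based imputation giving those subjects the placebo rate of 25%.

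Difference with them omitted: 0.45 − 0.25 = 20 points.

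Difference with them included: 0.45(1 − d) + 0.25d − 0.25 = 0.20(1 − d).

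Overstatement: 0.20d.

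| d (assumed) | NAL ER subjects omitted | Difference if included | Overstatement |
|---|---|---|---|
| 5% | 9 | 19 points | 1 point |
| 10% | 18 | 18 points | 2 points |
| 20% | 36 | 16 points | 4 points |
| 30% | 54 | 14 points | 6 points |

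Placebo loss does not change this comparison, because omitted placebo subjects are also taken to respond at 25%.

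**The case against.** The best defence is that SAP 12.3 calls itself guidance rather than exact code, and the filter has empty placeholders. The line introducing Step 1 speaks of visits from baseline onward; a filter that did so would keep everyone with a baseline row. This stands as far as it goes: the printed code does not prove what was run. It does not remove the defect, because the same introduction says its processes must be followed and gives no other rule for who enters the file.

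Second, the data sets may carry blank rows. SAP 7.4.1, 8.6 and 8.6.1.3 speak of setting values to missing, which could imply that rows exist. No data-set specification is in the documents, so this is open, and the point is conditional on it.

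Third, the loss may be small.

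- For WI-NRS under visits 2 to 5, a subject is lost only with no Week 2 or later average, and SAP 7.3.1 sets no minimum number of diary values for the Week 2 average.
- For ItchyQoL and PROMIS, the Off-Treatment visit collects both, and the SAP 7.2.7 windows assign Days 22 to 56 to Week 6. Only subjects with no questionnaire from Day 22 to the end of the Week 14 window are lost.
- Protocol 9.6 asks subjects who stop drug early to return at Week 14, and those who do stay in every version of the file.

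All of this limits the size. None of it provides for a subject with no value in the range.

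A reader might go further and infer that early dropouts cannot enter any of the imputations, or might treat TR03 non-completion (6 of 18 on NAL ER, 2 of 22 on placebo, from protocol 13.1) as the TR11 missing rate and quote a definite bias. The documents do not support either. The boundary differs by analysis, blank rows are not ruled out, TR03 non-completion is not a missing Week 14 value in TR11, and nothing says what share of loss falls before Week 6.

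**Conclusion.** The specification is wrong as written. Subjects and baselines both come from filtered post-baseline rows, so, absent blank visit rows, mITT subjects with no value in the range are left out. The range is Weeks 6-14 for Step 1, control-based imputation and ADQS, and Weeks 2-14 for the WI-NRS tipping-point code and the ADEFF text. This contradicts SAP 6.1, the scope stated in SAP 8.6, the Week 2 handling in SAP 8.6.1.2, and Step 3's own rule for Visit 3.

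The consequence falls on the control-based analysis, which should move these subjects toward control, and on the tipping point, which should shift them by delta. Simple imputation under missing at random would hardly change, because subjects with only a baseline are filled from their own arm's pattern. The main PAS item 5a analysis counts a missing Week 14 as non-response and is unaffected.

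The 1 to 6 point range is a scenario, not an estimate of bias. It rests on the assumed 5% to 30% NAL ER loss, the design response rates among retained subjects, and imputation at the placebo rate.

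**What to change.** Revise SAP 12.3 as follows.

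1. Start each imputation file from the mITT list, one row per subject, with arm, baseline and region from subject-level data.
2. Left-join the visit values so that missed visits stay blank. Do this for ADEFF and ADQS and for all three methods.
3. Use one visit range per endpoint throughout, reconciling visits 3-5 with visits 2-5 for WI-NRS.
4. Let the control-based step impute Visit 3 where missing, and Visit 2 for ADEFF, before Visits 4 and 5. Remove the expectation that Visit 3 is already complete.
5. Check that each of the 50 imputed data sets contains every mITT subject in each arm, and report by arm how many have no post-baseline value.

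The cost is a few lines of code and one count check. The sensitivity results may become slightly less favourable to NAL ER.

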To mitigate opioid-related side effects, NAL ER will be initiated with a titration schedule for 2 weeks in a double-blinded manner until the target dose is reached. Titration is a clinical management strategy consistent with dosing of opioids in general²⁶. The titration regimen planned in this study is similar to the regimen used in Phase 2 studies in UP and PN, in which doses in the planned range were well tolerated. In this study, the combination of a low starting dosing (27 mg NAL ER on the first day) followed by a relatively slow titration is expected to minimize treatment-limiting opioid adverse effects.

It is known from prior studies, that GI adverse effects (e.g., nausea and vomiting) and CNS adverse effects (e.g., dizziness, somnolence, and headaches) occur early and can be treatment-limiting. In anticipation of the possible occurrence of these effects, pre-medications for these symptoms will be permitted.

In anticipation of the possible occurrence of CNS AEs such as somnolence, subjects will be instructed to be aware of possible CNS AEs that may occur. The evening doses during the titration period should be taken at home. The first dose of any new titration step will occur with an evening dose (see “Instructions for Taking TR11 Study Medication”). Subjects will be instructed that the investigational product may impair mental and/or physical abilities required for the performance of potentially hazardous tasks such as driving a car or operating machinery, especially during the titration period and in combination with alcohol or tranquilizers or other pharmacologic CNS depressants. Subjects will be instructed not to drive or operate machinery unless they are tolerant to the drug and know how they will react to the medication. In discussing potential participation in this study with their subjects, Investigators and site staff should ensure that they understand the lifestyle of each individual, the nature of his or her professional activities, and any medication prohibitions or toxicology screening requirements that may be associated with his or her employment. The assessment should address the overall suitability of the subject for this study based on the safety considerations noted above.

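### SAP 12.3 says the WI-NRS imputation uses Week 2, but its printed models leave Week 2 out; any resulting bias in these sensitivity analyses has no known direction

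*SAP*

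**What the plan says.** SAP 12.3 describes three procedures: simple multiple imputation, control-based imputation and a tipping-point analysis. Its introduction fixes the WI-NRS visits: "ADEFF will use 4 visits (AVISITN 2-5/ Week 2, 6, 10, 14". ADQS, which holds the questionnaire scales, is limited to Weeks 6, 10 and 14.

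The steps that follow read differently:

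- **Simple imputation, Step 1:** "For this study, the missing data patterns will be checked by treatment and visits 3 to 5". The data step carries the same filter, and baseline is then taken from the filtered set.
- **Simple imputation, Steps 2 and 3:** the MCMC step runs on Visits 3 to 5. The regression is "var trt01pn base v3 v4 v5", with the stated rule "Visit 3 values are imputed using baseline value and treatment".
- **Control-based imputation:** the regression for Week 10 uses baseline and Week 6, and the step is then repeated for Week 14. The text expects every Week 6 value to be present by then.
- **Tipping point:** Week 2 is read in and the MCMC step has "var Visit2 – Visit5", but the regression returns to "var trt01pn base v3 v4 v5". SAP 8.6.1.2 meanwhile describes shifting an imputed Week 2 value.

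SAP 7.3.1 already derives the Week 2 average, from Study Days 8 to 14.

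**The concern.** The appendix describes missing at random as missingness that depends only on observed responses. For a subject with no itch average after Week 2, that average is the only post-baseline one. A model that omits it does not condition on the data its own assumption relies on.

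The documents give two routes to this pattern. Protocol 9.3 says that gastrointestinal and CNS effects "occur early and can be treatment-limiting", so some subjects may leave around titration. SAP 8.6.1.3 sets efficacy data to missing once a listed medication starts, and its list includes topical corticosteroids, antihistamines and capsaicin. Protocol 10.6.4 allows these for debilitating itch in the first 10 weeks. SAP 9 says the simple imputation models were added for this medication-related missingness. On the second route, itch itself can cause the missing value.

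At stake is the credibility of the sensitivity analyses. The tipping-point shifts start from the simple-imputation values, so a misplaced starting point carries through.

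**Working it through.** **1. Is the omission real for WI-NRS?** Visits 3 to 5 would be right for ADQS, so Steps 1 to 3 could be a template for those scales. They are not only that: Step 3 ends by writing the imputed columns to WINRSA, and the tipping-point regression, which is explicitly for WI-NRS, has the same variable list.

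**2. Does Week 2 in the tipping-point MCMC step rescue it?** No. That step fills only intermittent gaps. A subject with Week 2 observed and Weeks 6 to 14 missing is already monotone, so nothing is filled, and the regression then ignores Week 2. A flag for an imputed Week 2 is created, but the shift steps start at Week 6.

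**3. Does the control-based text cover a missing Week 6?** No. The same MCMC option leaves monotone gaps open, so the expectation that all Week 6 values are present fails for early dropouts, and no step imputes them.

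**4. How large could the effect be?** The documents give no figure for this. The responder rates used in the simulation were first checked against the plan's sample size (SAP 5.2). With 25% versus 45%, 90% power, two-sided 0.05 and mean rate 0.35:

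n per arm = [1.960 × √(2 × 0.35 × 0.65) + 1.282 × √(0.25 × 0.75 + 0.45 × 0.55)]² / 0.20² = (1.322 + 0.845)² / 0.04 ≈ 117.4

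This rounds up to 118, or 236 in total, against the SAP's 117 and 234.

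Sequential regression imputation was then run on 400,000 simulated subjects per arm, with and without Week 2 as a predictor.

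- *From the documents:* 25% and 45% responders. The upper dropout case uses TR03 non-completion (Protocol 13.1): (18 - 12)/18 = 33.3% for NAL ER and (22 - 20)/22 = 9.1% for placebo, all assumed to occur before Week 6.
- *Assumed:* baseline 8.3 (SD 0.9); SD of the itch reduction 1.5 at Week 2 and 2.5 at Week 14; Week 2 to Week 14 correlation 0.3 or 0.6; other dropout pairs (NAL ER/placebo) 10%/5% and 20%/5%; where dropout depends on Week 2 itch, log-odds change by 1 per SD.

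Bias = estimated minus true responder difference (true value about 20 points):

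| Dropout before Week 6 | Without Week 2 | With Week 2 |
|---|---|---|
| Depends on arm and baseline only | -0.1 to +0.1 | -0.1 to +0.1 |
| NAL ER dropouts had worse Week 2 itch | +1.1 to +6.8 | 0.0 to +0.1 |
| Dropouts in both arms had worse Week 2 itch | +0.6 to +5.4 | -0.1 to 0.0 |
| NAL ER dropouts had better Week 2 itch | -1.1 to -6.7 | -0.1 to +0.1 |
| Only placebo dropouts had worse Week 2 itch | -0.4 to -1.3 | -0.1 to +0.1 |
| NAL ER dropouts worse, but all stop before Day 8 | +1.1 to +6.6 | +1.0 to +6.6 |

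Positive values favour NAL ER. When only NAL ER dropout depends on Week 2 itch, the size is roughly the NAL ER dropout fraction times the error in the imputed response rate among those dropouts. At 33.3% dropout, correlation 0.3 gives 3.24/0.333 = 9.7 points per dropout, and correlation 0.6 gives 6.75/0.333 = 20.3.

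**The case against.** A reader might infer that the omission tilts the imputation towards NAL ER. The documents do not support that. The Protocol 9.3 remark concerns nausea, vomiting, dizziness, somnolence and headache, not itch. Protocol 13.1 likewise ties early dropout to opioid-initiation symptoms, and Protocol 10.6.4 reports that the TR03 arms separated on itch only between Weeks 4 and 6. If tolerability alone drives dropout, Week 2 itch need not matter. The medication route could produce more missing data in either arm. This objection stands: no sign can be asserted.

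Stopping drug is also not the same as missing data. Protocol 9.6 asks such subjects to return at Week 14, and the SAP's general study design calls for all remaining visits. Those who return can have an observed Week 14 value. This also stands, and it limits how many subjects are affected.

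The consequence is bounded. The SAP's primary analysis imputes nothing, control-based imputation draws NAL ER dropouts from placebo data, and the tipping-point shifts of 0.25 to 1 SD in both directions already probe a misplaced reference.

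Finally, the appendix calls itself guidance rather than exact code. That is weaker: it also says its processes and principles must be followed, and the Week 6 rule is one of them. It conflicts with the four-visit statement in the same appendix.

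**Conclusion.** The contradiction within SAP 12.3 holds. As printed, the WI-NRS imputation models discard an observed and already derived predictor, and the control-based procedure has no rule for a missing Week 6 value. The result is wasted information and a possible bias confined to sensitivity analyses.

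The bias is about nil if dropout depends only on arm and baseline. Otherwise it lies between -6.7 and +6.8 points on a true difference of 20, under the stated assumptions. Its direction is unknown, because no passage says how Week 2 itch relates to missingness. The extremes need correlation 0.6 and TR03's total non-completion all falling before Week 6, so they are upper cases.

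Adding Week 2 brings the bias to 0.14 points or less where a Week 2 average exists. It does nothing for subjects whose entries end before Day 8.

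One further risk depends on how ADEFF is built. If it holds no rows for missed visits, the Step 1 filter would remove early dropouts from the simple imputation rather than impute them.

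**What to change.** For WI-NRS only:

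1. Set the Step 1 filter and pattern check, and the Step 2 MCMC, to visits 2 to 5. Take baseline from a source that keeps subjects with no later visit in the data set.
2. In the simple and tipping-point regressions use `var trt01pn base v2 v3 v4 v5`, and state that Week 6 is imputed from baseline, treatment and Week 2.
3. In the control-based analysis add Week 2 without treatment: `var base v2 v3` for Week 6, then `var base v2 v3 v4`, and so on. Treatment cannot enter there. Each set holds controls plus only those NAL ER subjects missing that visit, so its effect could not be estimated, and including it would defeat imputation from controls.
4. Add the missing control-based step that imputes Week 6 from controls, and say how a subject with no Week 2 average is handled.
5. Reconcile the tipping-point shift code with the Week 2 shift described in SAP 8.6.1.2.

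Leave ADQS at Weeks 6 to 14; the Protocol's Table-1 schedules none of those scales at Week 2. The cost is a few edited lines across the three procedures, with no new data or derivation.
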